1.3.2 Clinical Experience of Acalabrutinib in CLL

Acalabrutinib has been administered to participants in clinical studies, including subjects with hematologic malignancies, solid tumors, or rheumatoid arthritis, and participants who are healthy volunteers or with mild to moderate hepatic impairment. No SAEs have been reported in the hepatic impairment study or in the healthy volunteer studies. No expected serious adverse reactions have been identified for acalabrutinib to date. For more detailed information on the clinical experience for acalabrutinib, please refer to the Investigator Brochure.

1.4 SUMMARY AND CONCLUSIONS

This study will evaluate the safety and activity of a potent, second-generation Btk inhibitor, acalabrutinib, versus ibrutinib in subjects with previously treated CLL with high-risk cytogenetics. The design and conduct of this study is supported by an understanding of the natural history and current therapies for subjects with CLL; knowledge of the activity and safety of the first-generation BCR inhibitor (ie, ibrutinib) in subjects with B-cell malignancies; and the available nonclinical and clinical information regarding acalabrutinib. Clinical studies have

shown that acalabrutinib is an orally bioavailable Btk inhibitor with fast absorption and rapid clearance that maintains optimal target coverage over 24 hours with a dosage of 100 mg BID. Acalabrutinib has been well tolerated in healthy volunteers and subjects with CLL or Richter's syndrome. Despite poor prognostic characteristics in the CLL study population, acalabrutinib has induced sustained decreases in lymphadenopathy and provides more rapid reduction and/or resolution of lymphocytosis than ibrutinib. No specific drug-related toxicity has been identified to date for acalabrutinib.

2 STUDY RATIONALE

This randomized controlled Phase 3 study is designed to assess whether acalabrutinib is non-inferior to ibrutinib with respect to PFS in subjects with previously treated CLL who have high-risk prognostic factors per NCCN guidelines ([NCCN Version 1.2016](#)).

2.1 DOSE SELECTION RATIONALE FOR ACALABRUTINIB

Preliminary PK data from ACE-CL-001 suggests a plateauing of exposure after 250 mg QD. PD results from this study also suggest Btk resynthesis occurs in malignant B cells within 24 hours. While all dosages evaluated show full Btk occupancy 4 hours after dosing, the 100-mg BID cohort shows full target coverage over 24 hours ($\geq 97\%$ Btk occupancy at 4 and 24 hours). Therefore, based on PK/PD and efficacy results of the Phase 1/2 study, acalabrutinib 100 mg BID will be evaluated in this Phase 3 study. This regimen is expected to provide optimal target coverage with lower exposure levels (C_{max}) of acalabrutinib to avoid any potential off-target effects from acalabrutinib.

2.2 NON-INFERIORITY DESIGN AND IBRUTINIB AS COMPARATOR

Assessment of the non-inferiority of acalabrutinib relative to ibrutinib, the reference Btk inhibitor, as therapy for patients with previously treated CLL is the most appropriate approach to describing the therapeutic characteristics of acalabrutinib in this treatment setting. Consistent with increasing scientific discussion regarding comparative effectiveness studies in oncology ([Hahn 2012](#)), such a study provides efficacy and safety information that is most relevant to patients, clinicians, regulatory authorities, and health economists in addressing the question of whether the clinical benefit of acalabrutinib can reasonably substitute for that of ibrutinib. The design of such a study offers many strengths that conform to the FDA draft guidance regarding non-inferiority studies ([FDA March 2010](#)):

- The benefit:risk of ibrutinib has been established in a large (N=391), well-conducted, randomized, controlled registration study evaluating its therapeutic efficacy relative to

ofatumumab (Byrd 2014, Brown 2014). This pivotal trial of ibrutinib offers a strong foundation upon which to evaluate the non-inferiority (NI) of acalabrutinib.

- The ibrutinib study showed a large treatment difference in PFS and OS between ibrutinib and an active comparator, thus providing a basis for a non-inferiority margin in the planned trial of acalabrutinib.
 - In the registration study, ibrutinib therapy was associated with a very high ORR (43% to 68% by independent and investigator assessment, respectively), thus providing compelling supportive evidence of drug effectiveness that supplements the ibrutinib treatment effect on PFS.
 - Accrual to the ibrutinib trial occurred between June 2012 and April 2013, ensuring the relevance of the findings to the current practice of oncology and increasing the prospect of a valid constancy assumption between the former ibrutinib trial and the proposed acalabrutinib study.
 - The ibrutinib study data have been subjected to thorough FDA and European Medicines Agency (EMA) review for product labeling, ensuring the veracity of the results as the basis for considering a new comparative trial with acalabrutinib.
- Ibrutinib and acalabrutinib are covalent inhibitors of Btk and thus offer similar pharmacology as the basis for comparative efficacy and safety.
 - The proposed trial addresses the single-agent effects of each drug, thereby avoiding confounding factors that might arise from co-administration of other drugs for the therapy of CLL.
 - Due to greater selectivity for Btk inhibition, acalabrutinib may offer a safety profile distinct from ibrutinib that can be directly evaluated in the context of the proposed trial.

The planned NI margin is designed to evaluate the unique benefit:risk profile of an alternative Btk inhibitor, while ensuring preservation of substantial benefit of the reference drug, ibrutinib.

2.3 SELECTION OF THE PATIENT POPULATION

The presence of 17p del or 11q del is associated with the worst clinical outcomes in patients with CLL (Gonzalez 2011, NCCN Version 1.2016) with a median survival of < 2 years in the relapsed/refractory setting. Treatment with chemoimmunotherapy for patients with CLL and 17p del is suboptimal (eg, a median PFS of 11.3 months has been reported for front-line fludarabine, cyclophosphamide and rituximab [Hallek 2010]). The recent development of agents targeting BCR signaling has provided substantial improvement in clinical outcome for this aggressive

form of the disease. However, as noted in [Section 1.1](#), patients with 17p del have the poorest outcome on ibrutinib therapy and seem to have a high rate of Richter's transformation.

Study ACE-CL-006 will use eligibility criteria that are substantially similar to those used in the RESONATE study in addition to limiting enrollment to patients with high-risk prognostic factors. This will allow testing of the hypothesis that a more selective Btk inhibitor may lead to greater clinical benefit in high-risk patients including a reduction in the incidence of Richter's transformation.

2.4 BENEFIT/RISK

Acalabrutinib is a potent, orally available small-molecule inhibitor of Btk. In the Phase 1/2 study of acalabrutinib in subjects with CLL or Richter's syndrome (ACE-CL-001), no dose-limiting toxicities (DLTs) have been identified at dosages of ≤ 400 mg QD or 100 to 200 mg BID. To date, no specific drug-related toxicity for acalabrutinib has been identified. The ORR in the evaluable subjects in ACE-CL-001 is currently 94% with some subjects obtaining PRs after only 2 cycles of therapy. In summary, the preliminary data suggest that acalabrutinib is well tolerated and has robust activity as a single agent in the treatment of subjects with relapsed or refractory CLL including those with 17p del or 11q del. In addition, PK/PD results show the 100-mg BID regimen produces optimal target coverage over 24 hours (ie, more complete coverage of de novo synthesis of Btk), which may provide greater clinical benefit than the QD regimen of ibrutinib.

As described previously, ibrutinib is approved for the treatment of patients with previously treated CLL and patients with CLL with 17p del. The most common adverse reactions ($\geq 20\%$) in patients with CLL treated with ibrutinib are thrombocytopenia, neutropenia, diarrhea, anemia, fatigue, musculoskeletal pain, upper respiratory tract infection, rash, nausea, and pyrexia (IMBRUVICA package insert). Note: For detailed information on the management of these adverse reactions refer to the IMBRUVICA package insert.

3 STUDY OBJECTIVES

3.1 PRIMARY OBJECTIVE

To assess whether acalabrutinib is non-inferior to ibrutinib with respect to PFS, based on IRC assessment, in subjects with relapsed or refractory CLL with high-risk prognostic markers.

3.2 SECONDARY OBJECTIVES

3.2.1 Efficacy Objectives

To evaluate the benefit:risk of acalabrutinib versus ibrutinib in terms of:

- Grade ≥ 3 infections
- Richter's transformation
- Atrial fibrillation
- OS

3.2.2 Safety Objective

[figure not shown]
The safety and tolerability including adverse events (AEs) of interest and laboratory assessments

3.2.3 Exploratory Objectives

CCI
[Redacted text block containing multiple lines of blacked-out text]

4 STUDY DESIGN

This randomized, multicenter (ie, approximately 200 global centers), open-label, non-inferiority Phase 3 study is designed to evaluate the efficacy and safety of acalabrutinib versus ibrutinib in subjects with relapsed or refractory CLL who have high-risk prognostic markers (eg, 17p del and/or 11q del) per NCCN guidelines ([NCCN Version 1.2016](#)).

Figure 4-1. Study Schema

Approximately 500 eligible subjects will be randomized in a 1:1 ratio into 2 arms to receive either acalabrutinib 100 mg BID (Arm A; N=250) or ibrutinib 420 mg QD (Arm B; N=250).

This study will use an IWRS for randomization. Randomization will be used to minimize bias in the assignment of subjects to treatment groups, to increase the likelihood that known and unknown subject attributes (eg, demographic and baseline characteristics) are evenly balanced, and to enhance the validity of statistical comparisons across treatment groups.

Randomization will be performed stratified by the following factors:

- Presence of 17p del
- ECOG performance status (ECOG = 2 versus ECOG \leq 1)
- Number of prior therapies (1-3 versus \geq 4)

Subject participation will include a Screening Phase, a Treatment Phase, a Post-treatment Phase, and a Post-disease Progression Phase. The Screening Phase will last up to 28 days before first dose of study drug, during which the subject's eligibility and baseline characteristics will be determined. The Treatment Phase will last from randomization until study drug discontinuation. Subjects will receive study drug daily until disease progression or unacceptable toxicity. The Post-treatment Phase will follow subjects for disease progression or death, if they

discontinued study drug treatment due to unacceptable toxicity or any reason. Subjects who withdraw consent or are lost to follow will not be followed for disease progression or survival.

The Post-disease Progression Phase will begin once the IRC has confirmed that a subject has progressive disease. In this phase, subsequent anticancer therapy with start date of therapy, IWCLL indication for treatment initiation, additional malignancy occurrence, and subject survival status will be recorded. The Post-disease Progression Phase will continue until death, lost to follow up, consent withdrawal, or study closure, whichever occurs first. Survival status must be assessed, and the date of death must be documented for each subject randomized to treatment, regardless of whether or not the subject received treatment.

Assessment of response and progression will be conducted in accordance with the IWCLL 2008 criteria with the modification that treatment-related lymphocytosis in the absence of other signs or symptoms of disease progression will not be considered progressive disease. The Investigator will evaluate sites of disease by radiologic imaging (primary), physical examination or other procedures as necessary, review of hematology and serum chemistry results, and disease-related symptoms. The same methods of assessment used to assess disease at baseline should be used throughout the study. A central laboratory will perform all hematology testing for the primary endpoint analysis. The primary efficacy analysis will be based on assessment from an IRC. As part of the IRC review, radiographic evaluations assessed by independent central radiologists and hematology results from a central laboratory will be provided. Detailed procedures will be described in a separate charter. An independent DMC will be formed and constituted according to regulatory agency guidelines. Detailed information regarding the composition of the DMC and detailed DMC procedures will be provided in a separate charter. The DMC will review the safety data periodically and provide recommendations according to the charter.

The end of trial is defined as the point when the last subject on study has completed CCI of follow up or has been lost of follow up, whichever occurs first. *In the event that a rollover or safety extension study is available, subjects who remain in this study (Study ACE-CL-006) may be transitioned to such a study. Once all eligible subjects are moved to a rollover or safety extension study, Study ACE-CL-006 would be considered closed. Any subject who would be proposed to move to a rollover or safety extension study would be asked to sign an ICF for the rollover or safety extension study. The rollover or safety extension study would ensure treatment continuation with visit assessments per its protocol.*

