An ET visit is required for safety assessments for any subjects who permanently discontinue treatment for any reason, including disease progression. The ET visit should be performed within 7 days of the last dose of all study drugs, if possible, and is not required for subjects who discontinue from the study within 10 days of a scheduled study visit or if the ET visit would be performed within 14 days of the SFU visit.

A SFU visit should be conducted at 30 (+ 7) days after his or her last dose of all study drugs to monitor for resolution or progression of AEs and to document the occurrence of any new events,

regardless of whether the subject receives a new anticancer therapy or demonstrates disease progression within this time frame. Refer to [Appendix A](#) for the assessments required for the ET and SFU visits.

Survival

After progression, subjects will be contacted to assess survival status approximately every 12 weeks until death, withdrawal by subject, lost to follow-up, or study terminated by Sponsor, whichever comes first. At study closure, a survival sweep will be conducted. All subjects who are on study and not known to have died before the survival sweep will be contacted at that time.

Subsequent Anticancer Therapies

After study drug treatment is complete, the following information on subsequent anticancer therapies will be collected approximately every 12 weeks until death, withdrawal by subject, lost to follow-up, or study terminated by Sponsor, whichever comes first:

- Receipt of all subsequent anticancer therapies
- IWCLL indication for initiation of subsequent anticancer therapy
- Response to all subsequent anticancer therapies

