8.2 REASONS FOR STUDY EXIT

Reasons for study exit include:

- Subject's withdrawal of consent from study
- Decision by sponsor to terminate the study
- Subject lost to follow-up
- Death

In case a subject is lost to follow-up, every reasonable effort must be made by the study site personnel to contact the subject and determine the reason for discontinuation. The measures taken to follow up must be documented.

When a subject withdraws before completing the study, the reason for withdrawal *and scope of withdrawal (e.g., complete or only from treatment and/or protocol assessments)* must be documented in the CRF and in the source documents. Subjects who withdraw consent should still be encouraged to complete the safety follow-up assessments before withdrawing consent, but these assessments cannot be mandated once consent is withdrawn. *In cases of partial withdrawal of consent, subjects should be encouraged to allow future contact for survival follow-up.*

Subjects who are withdrawn or removed from study treatment will not be replaced.

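### Protocol Section 4 both ends and requires survival follow-up for lost and withdrawn subjects, and the survival sweep omits them, so deaths needed for OS can go uncounted

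*Protocol*

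**What the plan says.** Four places in the protocol govern survival follow-up.

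- **Section 4, stop rule:** "Subjects who withdraw consent or are lost to follow will not be followed for disease progression or survival". It separates neither partial from full withdrawal nor loss from withdrawal.
- **Section 4, requirement:** "Survival status must be assessed, and the date of death must be documented for each subject randomized to treatment", whether or not study drug was taken. The preceding sentence sets the end of the phase: "The Post-disease Progression Phase will continue until death, lost to follow up, consent withdrawal, or study closure, whichever occurs first".
- **Section 7.1, Survival:** "After progression, subjects will be contacted to assess survival status approximately every 12 weeks until death, withdrawal by subject, lost to follow-up", or until the sponsor ends the study. A sweep takes place at study closure: "All subjects who are on study and not known to have died before the survival sweep will be contacted at that time".
- **Section 8.2:** loss to follow-up and withdrawal of consent from the study are study exits. For lost subjects, "every reasonable effort must be made by the study site personnel to contact the subject and determine the reason for discontinuation". The scope of a withdrawal must be recorded, and "In cases of partial withdrawal of consent, subjects should be encouraged to allow future contact for survival follow-up".

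In the SAP, OS is an ITT endpoint (7.2.2) and stands fourth in the fixed-sequence test of secondary endpoints (2.6). Death from any cause is also a PFS event (7.1.1). Subjects who are lost or exit are censored at the last adequate IRC assessment for PFS (Table 2) and at the date last known alive for OS (Table 3). The final analysis uses data up to the data cutoff (2.5).

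**The concern.** For a lost subject, a site cannot both stop survival follow-up and document survival status. For a partial withdrawal, the stop rule in Section 4 ends the follow-up that Section 8.2 tries to keep. The sweep does not repair this: loss is a study exit, so a sweep of subjects on study misses those whose status is unknown. It is also tied to study closure, whereas the confirmatory OS test uses the data cutoff.

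At stake is how complete the death data are for a type I error-controlled endpoint. Censoring at loss is harmless when loss is unrelated to prognosis. Subjects who disappear after stopping drug or deteriorating may die at a higher rate than those who stay. The trial is open label, so such loss could differ by arm.

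**Working it through.** The main check is textual: apply each rule to three kinds of subject.

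1. **Lost to follow-up.** The Section 4 stop rule ends survival follow-up; the Section 4 requirement demands it; the Section 7.1 contacts stop; the sweep excludes the subject; Section 8.2 asks for efforts at contact but names no vital-status source. The rules conflict, and the practical result is unknown status.
2. **Partial withdrawal.** The stop rule, read literally, ends survival follow-up; the requirement demands it; Section 8.2 encourages it. The rules conflict.
3. **Full withdrawal of consent.** The stop rule applies, and Section 10.3 bars further data collection once permission to use health information is withdrawn. Ending follow-up is legitimate here. Only an explicit exception in the Section 4 requirement is missing.

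**PFS.** The plan's figure reproduces. The inputs are the margin 1.429, 1:1 allocation, true HR 1.0, one-sided alpha 0.025 and 80% power (Protocol 9.3, SAP 2.3).

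- Events = 4(1.960 + 0.842)² / (ln 1.429)² = 4 × 7.849 / 0.1274 ≈ 247, against about 250 planned.
- Power with d events = Φ(ln 1.429 × √d / 2 − 1.960). For d = 250: Φ(2.822 − 1.960) = 80.6%.
- If 10 deaths were missed evenly across arms and the cutoff did not move, d = 240: Φ(2.765 − 1.960) = 79.0%.

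The analysis is event-driven, so evenly missed deaths would mainly delay the cutoff. Table 2 also censors at loss or exit, at subsequent anticancer therapy, and for events immediately after two or more missed visits. Many recovered deaths would therefore not count as primary PFS events.

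**OS.** There is no OS event target. The documents give no loss rate, so only the mechanism can be shown. The assumptions are 35% mortality, a true HR of 1.0 before loss, 8% of one arm and 4% of the other lost at uniformly distributed times, and censoring at loss as in Table 3. A simulation compared the hazard ratio with censoring against the one with all deaths known.

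- Death hazard unchanged after loss: about 3.7% and just under 2% of deaths are missed, and the hazard ratio shift is essentially nil.
- Hazard doubled after loss: shift about 1.6%.
- Hazard tripled after loss: shift about 3%.

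These are illustrations under assumed rates, not estimates for this trial.

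**The case against.** The strongest reply is that the passages can be read together. The requirement in Section 4 closes with a clause about subjects who never received treatment. It may mean only that untreated randomized subjects count, with survival collected for everyone until they exit. The sentence before it and Section 7.1 use the same stopping points. Section 8.2 demands effort to reach lost subjects, so the stop rule may describe what happens once contact fails. OS comes last in the hierarchy and supports a claim only if every earlier test succeeds.

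That reading is plausible, but the text does not state it: the requirement has no exception, and the stop rule does not recognise partial withdrawal. Even on that reading, nobody who exits is swept, and no sweep is set for the cutoff at which OS is tested. The low rank of OS limits the consequence without removing it.

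The objection does stand against two stronger inferences:

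- A reader might infer that the primary PFS result is materially at risk. Table 2 censors most of these subjects whether or not the death becomes known.
- A reader might infer that missing 8% of deaths in one arm and 4% in the other moves the OS hazard ratio by about 4%, from 0.92/0.96 = 0.958. That ratio keeps the denominator fixed, whereas Table 3 censors lost subjects and so removes their person-time as well. Nor does losing 8% of subjects mean missing 8% of deaths, because deaths before loss are counted.

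**Conclusion.** The inconsistency is real, and its practical consequence is incomplete vital status for lost and partially withdrawn subjects. It bears mainly on OS; for primary PFS it is limited. Its size cannot be stated, because the documents available give no loss rate and nothing in them shows imbalance between arms. Loss unrelated to prognosis leaves the hazard ratio essentially unbiased. Bias requires loss that is informative and differs by arm, which an open-label design makes possible but does not establish. Full withdrawal of consent is not part of the defect. This is a cheap improvement, not a threat to the primary conclusion.

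**What to change.** - Reconcile Protocol Sections 4, 7.1 and 8.2 so that only withdrawal of consent for all follow-up ends survival follow-up. Subjects who are lost, or who withdraw only from treatment or assessments, stay in it.
- Extend the survival sweep to all randomized subjects, using public records where local law and consent permit. Run it at the primary data cutoff, with results in before database lock, and again at study closure.
- State in SAP Tables 2 and 3 how a death learned of after loss or exit is handled. At present the general rule (a death by the cutoff is an event) and the loss-or-exit row can be read in opposite ways. Without this, recovered deaths might still be censored.

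The cost is a protocol and SAP wording change with the usual ethics submission, and a one-time vital-status check at about 200 centers, with no added visits. Local privacy rules and full withdrawals will limit what can be recovered, so the number with unknown vital status should be reported by arm.
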